## 1.1 Schedule of Events

The Schedule of Events (SOE) is presented in [Table 1](#).

**Table 1 Schedule of Events for Study 2019nCoV-ICC-E-101**

	Study Day:	0	7	28	56	63	70	84	182 
	Window (days):	0	+ 3	+ 3	+ 5	+ 3	+ 5	± 7	± 14
	Study Visit:	1	2	3	4	5	6	7	8
Informed consent	X								
Medical history	X								
Inclusion/exclusion criteria, including determination of baseline seropositivity to SARS-CoV-2 based on SARS-CoV-2 vaccination documentation or history of prior SARS-CoV-2 infection	X								
Randomization	X								
Demographics	X								
Prior/concomitant medications	X	X	X	X	X	X	X	X 	X 
Vital signs measurements	X 	X	X	X 	X	X	X	X	X
Urine pregnancy test	X			X			X 		
Physical examination (at baseline and as required thereafter) 	X	X	X	X	X	X	X	X	X
Vaccination	X 			X 			X 		
Reactogenicity / Participant Diary Completion	X 	X		X 	X				
Blood sampling for SARS-CoV-2 (anti-NP) antibodies	X 					X		X	
Blood sampling for SARS-CoV-2 immunogenicity (ELISA), HAI serology, and influenza virus MN 50 assay (testing performed at Novavax)	X 		X	X 		X	X	X	
Blood sampling for SARS-CoV-2 MN 50 assay	X		X	X		X	X	X	
Whole blood sampling and PBMC harvest for SARS-CoV-2 spike-specific T cell counts at a pre-specified subset of sites 	X	X			X			X	
Unsolicited AEs	X	X	X	X	X	X			
MAAEs	X	X	X	X	X	X	X	X	X
SAE	X	X	X	X	X	X	X	X	X
AESIs (including PIMMCs)	X	X	X	X	X	X	X	X	X

ELISA = enzyme-linked immunosorbent assay; EoS = End of Study; HAI = hemagglutination inhibition; IFN $\gamma$  = interferon gamma; IL-2 = interleukin-2; MAAE = medically attended adverse events; MN = microneutralization; NP = nucleoprotein; PBMC = peripheral blood mononuclear cells; PCR = polymerase chain reaction; PIMMC = potential immune-mediated medical conditions; SAE = serious adverse event; SARS-CoV-2 = severe acute respiratory syndrome coronavirus 2; Th1 = Type 1 T helper; Th2 = Type 2 T helper; TNF $\alpha$  = tumor necrosis factor alpha.

1. Vital signs to be captured pre-vaccination and between 30 to 60 minutes post-vaccination.
2. Participants should be free of acute illness (defined as the presence of a moderate or severe illness in the clinical judgment of the investigator) with or without fever, or an oral temperature  $\geq 38^\circ\text{C}$  in order to receive the test article injection. Participants presenting with an acute illness on screening/Day 0 may return to the trial site within the next 7 days to receive their injection provided symptoms have resolved.
3. Starting on the first vaccination day (Day 0) and for 6 days thereafter (Day 0 through Day 6, inclusive), participants will maintain diaries for daily recording of their body temperature and any AE spontaneously offered (reactogenicity).
4. Starting on the second vaccination day (Day 56) and for 6 days thereafter (Day 56 through Day 62, inclusive), participants will maintain diaries for daily recording of their body temperature and any AE spontaneously offered (reactogenicity).
5. Participants presenting with an acute illness on Day 56 may return to the trial site within the next 7 days to receive their second vaccination. If a participant has experienced any AEs/AESIs/SAEs between trial Days 0 and 56, the Day 56 vaccination may be administered or delayed for up to 7 days based on the investigator's discretion.
6. Day 0 prior to vaccination.
7. Including IL-2, TNF $\alpha$ , CD40L, and IFN $\gamma$ .
8. EoS.
9. After physical examination at baseline determines eligibility, subsequent physical examination assessments are symptom directed as triggered by AE or symptom reports.
10. In order to receive a complete 2-dose series of COVID-19 vaccine, participants from treatment group O will receive a third dose of vaccine consisting of 5  $\mu\text{g}$  SARS-CoV-2 rS nanoparticle vaccine and 50  $\mu\text{g}$  Matrix-M1 at Day 70. Note that because Vaccine Group O is the only treatment group receiving a vaccine at Day 70, Vaccine Group O participants and site staff will

be unblinded to participant's treatment status from Day 70 onwards. The Sponsor recognizes this partial unblinding and assesses it as having minor impact to the data.

11. After Day 70, only those concomitant medications taken for any of the following events will be recorded: any MAAEs, SAEs, or AESIs (including PIMMCs).
12. Participants in Vaccine Group O who are women of childbearing potential will have a urine pregnancy test performed at the Day 70 visit prior to dosing.

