Study Design	
This is a randomized, observer-blinded, Phase 1/2 study evaluating the safety and immunogenicity of a quadrivalent hemagglutinin (HA) nanoparticle influenza vaccine (qNIV) and severe acute respiratory syndrome coronavirus 2 (SARS-CoV-2) recombinant spike (rS) nanoparticle combination vaccine with Matrix-M1™ adjuvant; this combination vaccine is referred to as Influenza COVID-19 Combination (ICC) vaccine.
 
The study will enroll approximately 640 healthy (based on history and physical examination) adult male and female participants 50 to 70 years of age, inclusive, targeting participants who are baseline seropositive (either previously infected with SARS-CoV-2 <math>\geq 8</math> weeks prior to enrollment, or have been previously immunized against SARS-CoV-2 with a completed regimen of an authorized vaccine at <math>\geq 8</math> weeks prior to enrollment). Randomization will be stratified on age <math>\geq 50</math> to <math><60</math> or <math>\geq 60</math> to <math>\leq 70</math> years to distribute the proportions of each age stratum evenly across vaccine groups.
 
Participants will be simultaneously enrolled and randomly assigned equally into 1 of 16 vaccine groups as per the Study Design Table below. The doses of the influenza and SARS-CoV-2 rS components included in the various vaccine groups have been selected based on the known performance of the antigens separately and the ability to obtain response data over a broad range of mixtures. These data will in turn be used in statistical modeling to predict one, or a few, optimal formulations for further clinical testing. All participants in Vaccine groups A through P will receive 2 intramuscular (IM) doses of the investigational combination vaccine, the first on Day 0 and the second on Day 56 (+ 5 days) and remain on study for immunogenicity and safety data collection through Day 182 (End of Study [EoS]); participants in Vaccine Group O will receive an additional IM dose of 5 <math>\mu</math>g SARS-CoV-2 rS with 50 <math>\mu</math>g Matrix-M1 adjuvant on Day 70 to ensure this group receives 2 doses of COVID-19 vaccine. The key informative immunogenicity time points for antibody responses will be Days 0 and 70 (14 days post-second dose), and for cell-mediated immunity (CMI) will be Days 0 and 63 (7 days post-second dose). Reference formulations of 60 <math>\mu</math>g HA/strain qNIV with 75 <math>\mu</math>g Matrix-M1 adjuvant and 5 <math>\mu</math>g SARS-CoV-2 rS with 50 <math>\mu</math>g Matrix-M1 adjuvant will be included as vaccine groups to benchmark optimal immune responses to each antigen administered as a standalone vaccine. The study will enable selection of one or more optimized ICC vaccine formulations (through Design of Experiments [DoE] response surface modeling) to advance into further development for dose/formulation confirmation in a future Phase 2 study.

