Target Population	
Adult participants <math>\geq 50</math> to <math>\leq 70</math> years of age who are baseline seropositive to SARS-CoV-2 defined as either:
 

Having completed a primary vaccination series against SARS-CoV-2 with an authorized COVID-19 vaccine with receipt of second/final dose of authorized vaccine <math>\geq 8</math> weeks prior to enrollment (first study vaccination).

 
OR
 

Previously infected with SARS-CoV-2 <math>\geq 8</math> weeks prior to enrollment (first study vaccination).

 
Baseline SARS-CoV-2 seropositivity determination at screening will be based on vaccination documentation (eg, vaccination cards or vaccination registry) or participant report of a previous SARS-CoV-2 infection.

Number of Participants and Dosing Regimens	Total: Approximately 640 participants Per treatment: Study Design Table							
	Vaccine Group	N	Day 0			Day 56 (+ 5 days)		
			HA Dose per Strain, µg	rS, µg	Matrix-M1, µg	HA Dose per Strain, µg	rS, µg	Matrix-M1, µg
	ICC vaccine formulations							
	A	40	60	22.5	50	60	22.5	50
	B	40	10	2.5	50	10	2.5	50
	C	40	60	22.5	50	60	22.5	50
	D	40	10	7.5	50	10	7.5	50
	E	40	10	22.5	50	10	22.5	50
	F	40	35	7.5	50	35	7.5	50
	G	40	5	22.5	50	5	22.5	50
	H	40	60	2.5	50	60	2.5	50
	I	40	5	7.5	50	5	7.5	50
	J	40	5	2.5	50	5	2.5	50
	K	40	35	22.5	50	35	22.5	50
	L	40	35	2.5	50	35	2.5	50
	M	40	60	7.5	50	60	7.5	50
	N	40	60	2.5	50	60	2.5	50
qNIV with Matrix-M1 adjuvant reference formulation								
	O 	40	60	0	75	0	5	50
	SARS-CoV-2 rS with Matrix-M1 adjuvant reference							
	P	40	0	5	50	0	5	50
	Total	640						
Abbreviations: COVID-19 = coronavirus disease 2019; HA = hemagglutinin; rS = recombinant spike protein; qNIV = quadrivalent hemagglutinin nanoparticle influenza vaccine; SARS-CoV-2 rS = severe acute respiratory syndrome coronavirus 2 recombinant spike protein nanoparticle vaccine.								
Length of Participation	1. Antigen and adjuvant dose values are nominal and reflect target doses. Details of the final product in-clinic mixing scheme, the actual content of doses achieved by the in-clinic mixing of drug product lots, and injected volumes used are provided in the Study Pharmacy Manual.							

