### 5.3 Inclusion Criteria

To be included in this study, each individual must satisfy all of the following criteria:

1. Healthy, medically stable adult male or females  $\geq 50$  to  $\leq 70$  years of age at screening.
2. Willing and able to give informed consent prior to study enrollment.
3. Able to attend study visits, comply with study requirements, and provide reliable and complete reports of AEs.
4. Participants must have been baseline seropositive to SARS-CoV-2 defined as either:
  - Having completed a primary vaccination series against SARS-CoV-2 with an authorized COVID-19 vaccine with receipt of second/final dose of authorized vaccine  $\geq 8$  weeks prior to enrollment (first study vaccination).

OR

- Previously infected with SARS-CoV-2  $\geq 8$  weeks prior to enrollment (first study vaccination).

**Note:** Baseline SARS-CoV-2 serostatus determination at screening will be based on vaccination documentation (eg, vaccination card or vaccination registry) or participants' report of a previous SARS-CoV-2 infection.

5. Women of childbearing potential (defined as any female participant who is NOT surgically sterile [ie, hysterectomy, bilateral tubal ligation, or bilateral oophorectomy] or postmenopausal [defined as amenorrhea at least 12 consecutive months]) must agree to be heterosexually inactive from at least 28 days prior to enrollment and through the end of the study OR agree to consistently use a medically acceptable method of contraception listed below from at least 28 days prior to enrollment and through the end of the study.
  - a. Condoms (male or female) with spermicide (if acceptable in country)
  - b. Diaphragm with spermicide

- c. Cervical cap with spermicide
- d. Intrauterine device
- e. Oral or patch contraceptives
- f. Norplant®, Depo-Provera®, or other in-country regulatory approved contraceptive method that is designed to protect against pregnancy
- g. Abstinence, as a form of contraception, is acceptable if in line with the participant's lifestyle

**Note:** Periodic abstinence (eg, calendar, ovulation, symptom-thermal, post-ovulation methods) and withdrawal are not acceptable methods of contraception. These procedures and laboratory test results must be confirmed by physical examination, by subject recall of specific date and hospital/facility of procedure, or by medical documentation of said procedure.

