### **9.2 Population**

#### **9.2.1 Sample Size Rationale**

The sample size of 40 participants per group for this study is based on clinical and practical considerations and not on a formal statistical power calculation. This distribution of participants would provide a sufficient number of replicates per set of factor levels studied in the DoE approach to account for expected variability in the immune responses due to elements such as subject and assay variability. There were no formal power calculations based on the DoE analysis methods. As an informal way to measure the approximate number of replicates (ie, participants) needed per vaccine formulation, the data from HAI testing with VLP reagents from the qNIV-E-301 study for eleven vaccine-homologous and vaccine-nonhomologous strains will be used to average the fold rise at Day 28 to provide input to a sample size calculation to detect a two-fold difference in response relative to baseline. This calculation showed that a sample size of 40 would provide > 99% power to differentiate the immune response between two formulations.

With 40 participants in each treatment group, there is 87% probability to observe at least 1 participant with an AE if the true incidence of the AE is 5%. With 560 participants receiving a combination formulation of influenza and SARS-CoV-2 vaccine, an AE with true incidence of 0.534% can be detected with 95% probability.

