Baseline anti-NP results will be summarized qualitatively and/or quantitatively by study vaccine group. A breakdown of baseline seropositivity may be summarized by study vaccine group to report the number and percentage of participants having a previous COVID-19 vaccination and/or reporting a previous SARS-CoV-2 infection. In addition, the time between prior exposure to SARS-CoV-2 (either first dose of vaccine or natural infection) and Day 0 may be summarized by study vaccine group using descriptive statistics (i.e. mean, median, standard deviation, minimum, maximum).

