7.2.2 ELISA (IgG) Concentration and MN_{50} Titers for SARS-CoV-2

Serum (IgG) antibody responses (ELISA) for vaccine homologous SARS-CoV-2 rS antigen and cross-reactive virus variants, if available, will be conducted. For the serum IgG antibody levels specific for the rS antigen(s) as detected by ELISA, the derived/calculated endpoints of IgG antibody response will include: GMEU, GMEUR, $GMFR_{Post/Pre}$, SCR, which will be calculated in manner similar to HAI antibodies described above. Further description of the analyses for GMEUR appear at the end of this section.

MN_{50} antibody responses for vaccine homologous SARS-CoV-2 rS antigen and cross-reactive virus variants, if available, will be conducted. The derived/calculated endpoints of MN_{50}

antibody responses specific for SARS-CoV-2 wild-type will include the same assessments of GMT, GMFR_{Post/Pre}, GMTR, SCR as HAI antibody response.

The definition of seroconversion is a post-vaccination concentration/titer \geq 4-fold higher than baseline. Participants indicating evidence of infection with SARS-CoV-2 prior to the time point analyzed may be excluded from the calculations. This will be determined by examining the anti-NP results taken at Day 70 and/or Day 182. An alternative measure, seroresponse, may be explored which is defined as participants having a value or fold-rise greater than the 95th percentile of values in a reference group, which would be chosen if this analysis is performed and described in the study report.

Between-group GMEUR of IgG and MN antibodies to SARS-CoV-2 will be calculated at post-vaccination time points (adjusted for intergroup variation in baseline [pre-vaccination] values) and two-sided 95% CI will be calculated on log-transformed values using the analysis of covariance (ANCOVA) with the study vaccine group and baseline (Day 0) measurement as the covariates under two-sided type I error rate of 0.05. No type I error rate will be adjusted.

- Groups A-N (experimental vaccine) individually after 1 dose at Day 28 to Group P (reference vaccine) after 1 dose at Day 28
- Groups A-N (experimental vaccine) individually after 2 doses at Day 70 to Group P (reference vaccine) after 2 doses at Day 70

Two-sided 95% CIs of the difference in SCRs for IgG and MN antibodies to SARS-CoV-2 for the above cited comparisons of GMEUR will be based on the Miettinen and Nurminen method with the following sample SAS code:

```
proc freq data=SARSdata;
  by Visit;

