As a parallel analysis, SAS PROC RSREG will be used to run a response surface model that uses the dataset without first averaging the results of each run across replicates nor incorporating the baseline measurement into a fold-rise (i.e. use the data as-is). In this model, Y would be set as the antibody response value at the time point of interest, with BL being the corresponding measurement at Day 0. X1 and X2 have the same definition as the when the model is fitted within SAS JMP.

Example SAS code:

```
PROC RSREG DATA=X;  
MODEL Y=BL X1 X2 / LACKFIT COVAR=1;  
RUN;
```

The fit of the model is to be assessed by examining the p-value from the lack-of-fit test and plots of residuals for each factor. Significance of main, quadratic and interaction effects will also be assessed and reported.

The canonical analysis results from PROC RSREG provide information on the shape of the response surface. A maximum point is identified on the response surface by all eigenvalues being negative (a second order derivative test).

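### Day 0 anti-NP, a pre-vaccination marker of past SARS-CoV-2 infection, is drawn in everyone but only tabulated; prespecify it as a covariate beside the Day 0 value in the SARS-CoV-2 models.

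*Protocol*

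**What the plan says.** - **Eligibility (Protocol Synopsis, Target Population; 5.3).** A participant enters either through "Having completed a primary vaccination series against SARS-CoV-2 with an authorized COVID-19 vaccine" at least 8 weeks before enrollment, or through SARS-CoV-2 infection at least 8 weeks before. The evidence is "vaccination documentation (eg, vaccination card or vaccination registry) or participants' report of a previous SARS-CoV-2 infection". Having both is not excluded.
- **Randomization (Synopsis; 7.2.2).** Stratified by two age bands, "to distribute the proportions of each age stratum evenly across vaccine groups". Priming history is not a stratification factor.
- **Sampling (Table 1 and its footnote 6; 6.1.1).** "Blood sampling for SARS-CoV-2 (anti-NP) antibodies" is scheduled on Days 0, 70 and 182; the Day 0 sample precedes vaccination.
- **Baseline tables (SAP 5).** "Baseline anti-NP results will be summarized qualitatively and/or quantitatively by study vaccine group". A breakdown by previous vaccination and reported infection is optional.
- **Between-group ratios (SAP 7.2.2, 11.2).** GMEUR/GMTR come from "log-transformed values using the analysis of covariance (ANCOVA) with the study vaccine group and baseline (Day 0) measurement as the covariates". Section 11.2 names only the pre-vaccination titre.
- **Response surface (SAP 7.4).** The JMP fits start from participant fold-rise, with the Day 0 value as an optional covariate when replicates are not averaged. The parallel SAS fit is "MODEL Y=BL X1 X2 / LACKFIT COVAR=1", where BL is the Day 0 value of the response.
- **Later anti-NP (SAP 7.2.2, 7.4).** May be used to exclude participants infected on study.

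**The concern.** Two participants can have the same Day 0 anti-S titre, one after recent vaccination and one after infection. If their recall responses differ, titre adjustment cannot separate them, and anti-NP might. SAP 7.4 already treats infection between Day 0 and Day 70, detected by anti-NP, as extra variability worth removing. No prespecified model accounts for infection before Day 0, although the marker is measured then.

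At stake is precision in the ICC-versus-P ratios and, to a lesser degree, in the fitted rS/HA surface, both of which inform formulation selection. All ICC groups are compared with the same Group P, so a chance excess or deficit of previously infected participants in P moves every ratio in the same direction.

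**Working it through.** **The plan's own precision figure.** Protocol 9.2.1 states that "The sample size of 40 participants per group for this study is based on clinical and practical considerations" and gives an informal power above 99% for a two-fold difference at n = 40, based on HAI data. It gives no SD, so the figure cannot be reproduced. With a two-sided normal approximation, power = Φ(log10 2 / (SD·√(2/40)) − 1.96). This gives 99.4% at log10 SD 0.3, 92.0% at 0.4 and 76.8% at 0.5. Power above 99% needs an SD of about 0.314 or less.

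**Inputs.** From the documents: 40 per group; 14 ICC groups, of which five have rS 22.5 µg (A, C, E, G, K) and five have rS 2.5 µg (B, H, J, L, N). Assumed, because the documents give none of them: share anti-NP positive p = 5%, 20%, 40%; effect of past infection at equal Day 0 titre F = 1.5- or 2-fold; log10 SD 0.4.

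**Formulas.**
1. 95% chance imbalance between two groups of 40: d = 1.96·√(2p(1−p)/40).
2. Resulting shift in a GMEUR: F^d.
3. Removable share of variance: p(1−p)(log10 F)²/0.4², taking 0.4 as the total SD.

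| p | d (points) | Shift, F = 1.5 | Shift, F = 2 | Variance, F = 1.5 | Variance, F = 2 |
|---|---|---|---|---|---|
| 5% | 9.6 | 1.04 | 1.07 | 1% | 3% |
| 20% | 17.5 | 1.07 | 1.13 | 3% | 9% |
| 40% | 21.5 | 1.09 | 1.16 | 5% | 14% |

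If 0.4 is instead the SD within infection strata, the denominator becomes 0.4² + p(1−p)(log10 F)². The top figure then falls from 14% to 12%.

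**Middle case (p = 20%, F = 2, within-stratum SD 0.4).** The variance from past infection is 0.16 × 0.301² = 0.0145, and 0.0145/(0.16 + 0.0145) = 8.3%. Adjustment changes the 95% CI factor on a ratio, 10^(1.96·SD·√(2/40)), from 1.52 to 1.50. Power for two-fold rises from 89.7% to 92.0%. This is worth 40/(1 − 0.083) = 43.6 participants per group instead of 40.

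**Group P alone, same inputs.** 1.96·√(0.16/40) = 12.4 points, and 2^0.124 = 1.09, common to all ICC-versus-P ratios.

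**Response surface, same inputs.** Highest against lowest rS dose has 5 × 40 = 200 per side. 1.96·√(2 × 0.16/200) = 7.8 points, and 2^0.078 = 1.06.

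**Lower end.** With p = 5% and F = 1.25, 0.3% of variance is removed and nothing changes in practice.

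**The case against.** The strongest reply is that the plan already does most of this. The ANCOVA and the SAS fit adjust for the Day 0 value, and the JMP fit uses fold-rise or an optional baseline covariate. Baseline anti-NP is tabulated, so an imbalance would be seen. The documents offer no evidence that infection matters at equal titre, the analyses are descriptive, and in the middle case the CI factor barely moves. All of this stands, and it limits the point to a modest gain in precision. It does not remove the point: tabulation shows an imbalance without correcting it, and adding the term after the Day 70 unblinding would be a data-driven choice.

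A reader might infer more than the documents support:

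- *That priming history is left wholly as noise.* It is not; only the part not carried by the Day 0 value remains.
- *That the ratios are biased.* Chance imbalance under randomization is random error, which the interval from the planned model already covers.
- *That the groups-of-40 figures apply to the surface.* The surface pools 14 groups.
- *That anti-NP separates infection-primed from vaccine-primed participants.* It marks infection; a participant may have had both.
- *That the covariate is pre-randomization.* The documents show only that the sample precedes vaccination, and Protocol 6.1.1 lists randomization before the blood draw. It is still a valid baseline value.

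**Conclusion.** The point holds as a missed, inexpensive gain in precision. It is neither a source of bias nor a contradiction in the plan. Day 0 anti-NP is collected in everyone, and no prespecified SARS-CoV-2 model uses it. The size rests entirely on assumed values for the share positive, the effect at equal Day 0 titre and the SD. Across the tabulated range the gain is small to modest, and it is nil if almost nobody is positive. The case for acting is strongest for the ICC-versus-P ratios, which share one reference group of 40, and weaker for the surface.

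**What to change.** - **SAP 7.2.2 and 11.2.** Prespecify Day 0 anti-NP status, positive or negative by the assay's cutoff, as a fixed effect beside the Day 0 log value in the GMEUR/GMTR ANCOVA for anti-S IgG and SARS-CoV-2 MN50. State the cutoff, which the documents do not give.
- **SAP 7.4.** Add the same term to the participant-level anti-S fits in both JMP (the main DoE tool under SAP 10) and PROC RSREG. RSREG has no CLASS statement, so code NP as numeric 0/1: `MODEL Y=BL NP X1 X2 / LACKFIT COVAR=2`. If any Day 0 anti-NP result is missing, add a numeric missing indicator to the covariates and use `COVAR=3`. The term does not apply to fits on averaged runs.
- **Sensitivity.** Keep the fit adjusted for baseline titre alone. State before unblinding that the term is dropped if almost no participant is anti-NP positive, with the minimum count fixed in advance.

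The cost is 1 degree of freedom (2 with a missing indicator) and minor SAP wording. No new sample or visit is needed.
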